4.4. Randomization

A block randomization schedule - to ensure balance of the two arms among the study sample, stratified for the two species of Schistosomiasis, will be prepared by the sponsor biostatistician. The individual randomization number and treatment arm of each subject will be stored in sealed envelopes.

Randomization will be done at the time of enrollment using randomization envelopes, specifying the treatment arm. This is an open-label study, so both the study team members as well as the participant will immediately be informed about the assignment to one of the two study arms. The randomization list will be prepared using SAS 9.4 (SAS Institute, Cary NC).

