infection rapidly spread throughout the northern region. A decade later, this severe *S. mansoni* epidemic was followed by a shift towards *S. haematobium* infection, which also reached record prevalences. Today, schistosomiasis is still highly endemic in Senegal, despite national control efforts. Both *S. mansoni* and *S. haematobium* are wide-spread, resulting in a large number of people with mixed infections in the communities ⁷.

Since the 1970s, treatment schistosomiasis has relied almost exclusively on praziquantel (PZQ). PZQ has demonstrated good efficacy ¹ in a meta-analysis of 55 comparative and non-comparative trials involving > 19,000 participants, of whom 68% were school-age children ⁸; results can be summarized as follows:

- For *Sh* infection, the WHO-recommended 40 mg/kg single dose of PZQ achieved a cure rate (CR) of 77.1% (95% confidence interval [CI] 68.4-85.1%; 2,645 participants/20 studies) and a mean egg reduction rate (ERR) of 94.1% (1,957 participants/19 studies).
- For *Sm* infection, the WHO-recommended 40 mg/kg single dose of PZQ achieved a CR of 76.7% (95% CI 71.9-81.2%; 6,377 participants/45 studies) and a mean ERR of 86.3% (5,546 participants/39 studies).
- For mixed Sh/Sm infection, CR was 63.5% (95% CI 48.2-77.0%; 379 participants/6 studies).

Another meta-analysis comparing school-age and preschool-age children in 47 comparative/noncomparative studies showed similar efficacy results in both age groups ⁹. The WHO has set a tentative ERR threshold of 90% as an indicator of optimal efficacy ¹⁰. In a systematic review of 10 studies, CR and ERR of *Sm* infection increased with repeated PZQ administrations, but such an effect was not observed for *Sh* ¹¹.

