4.2. Inclusion and exclusion criteria

Inclusion criteria

- 1. Children ≥ 6 and ≤ 14 years of age
- 2. Enrolled in one of the selected primary schools in the district of Richard Toll
- 3. Infected with schistosomiasis (i.e. presence of Schistosoma spp. eggs in urine and/or stool)
- 4. Informed consent from parents/guardians signed

Exclusion criteria

- 1. Planned travel of more than 1 months within the first 4 months after enrolment
- 2. History of, or ongoing, epilepsy or psychiatric illness (i.e. recent history of depression, generalized anxiety disorder; history of psychosis, schizophrenia or other major psychiatric disorders) or known hypersensitivity to one of the three study drugs
- 3. Chronic medication for any reason
- 4. Any severe underlying illness, including severe malnutrition or severe chronic schistosomiasis, based on clinical judgement
- 5. Any febrile illness or clinical malaria
- 6. Exposure to PZQ or ACT within the three previous months.

As mentioned above, children with schistosomiasis but excluded from the study will be treated with PZQ according to standard of care in Senegal. Children found with other illnesses or severe schistosomiasis will be referred to adequate health facilities for further care.

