4.3. Sample size

The sample size was calculated on the parasitological cure rate endpoint after the first course of AM, to test the hypothesis that AM is non-inferior to PZQ: at least a 65% cure rate with AM as compared to a 75% cure rate with PZQ according to the following rationale. We consider that a cure rate (CR) of 65% is clinically acceptable as threshold for non-inferiority for the AM combination, for the following reasons: a cure rate above 65% would be very satisfactory compared to all alternative drugs evaluated so far against schistosomiasis, and an efficacy slightly lower than that of PZQ would be largely compensated by the positive clinical effect due to concomitant malaria suppression. Note that this is likely to be marginal in North Senegal where malaria transmission is low, but this "dual" effect could be a major added-value in many other co-endemic regions with higher malaria transmission

Sample size was calculated by simulation to obtain 80% power. The required sample size is 300 schoolchildren per arm. To account for a 20% loss to follow up, the total number of children to be recruited will be 726 (363 per arm). With the same sample size, superiority of repeated courses of AM to PZQ (cure rate of at least 85% after 3 courses) can also be demonstrated with a similar power (i.e. secondary endpoint).

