8.2. Variables of interest

Primary

The primary variables to evaluate are:

- The parasitological cure rates (proportion of subjects negative for both *Schistosoma* species assessed by microscopy over total number in each arm) for AM and PZQ at week 4 after inclusion.
- The patient counts with drug-related adverse events and serious adverse events up to 4 weeks after AM and PZQ administration.

Secondary:

The secondary variables to evaluate are:

- The proportion of cured subjects (CR) of the two different arms at week 10, 16, 24 and 48 (see flowchart).
- The count of patients reporting any form of adverse event up to 4 weeks after each study drug administration.
- The egg reduction rate (ERR) at weeks 4, 10, 16, 24 and 48 (see flowchart). The ERR will be expressed as the percentage of eggs present in each subject at each time point over the number of eggs at baseline.
- The cure rate and egg reduction rate at weeks 4, 10 and 16 after first treatment administration by *Schistosoma* species and by intensity of infection.
- The result of the classic and novel diagnostic tests at baseline and at different time points, as well as a-composite reference standards.
- Clinical and laboratory characteristics related to schistosomiasis-related morbidity at baseline and at weeks 4, 10, 16, 24 and 48
- Prevalence of malaria infection at baseline and at weeks 24 and 48
- The incidence of clinical malaria during the study until week 48
- Counts of cases of anemia both pooled and by severity levels at baseline, week 24 and week
 48
- Binary variables indicating the existence of any or specific types of resistance in the sample size and among the incident malaria cases

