8.3.3. Primary analysis

The primary hypothesis for non-inferior efficacy will be assessed by calculating the two-sided 95% confidence interval (CI) for the difference in proportions of cured subjects. The CI will be calculated using Wilson's score method.

Interpretation of the CI will be as follows:

- if the two-sided 95% CI for the difference in cure rates (AM schedule PZQ schedule) lies entirely above -10% then non-inferiority of the AM schedule is concluded;
- if the 95% CI for the difference in cure rates includes -10%, then non-inferiority cannot be established;
- if the 95% CI for the difference in cure rates lies entirely below -10%, then the AM regimen is clinically inferior to the standard regimen.

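### Randomisation is stratified by Schistosoma species but the primary non-inferiority interval is not, and the placing of mixed infections is left open: a free improvement with a small gain

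*Protocol*

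**What the plan says.** - **Randomisation (4.4).** The list is "stratified for the two species of Schistosomiasis, will be prepared by the sponsor biostatistician". The strata are not spelled out further.
- **Eligibility (4.2).** Infection means "presence of Schistosoma spp. eggs in urine and/or stool", so a child may carry *S. haematobium* (Sh), *S. mansoni* (Sm) or both. Section 1.1.1 says both species are widespread in Senegal, "resulting in a large number of people with mixed infections in the communities", but gives no percentage.
- **Endpoint (8.2).** Cure is the "proportion of subjects negative for both" species by microscopy at week 4.
- **Primary analysis (8.3.3).** The hypothesis is tested by "calculating the two-sided 95% confidence interval (CI) for the difference in proportions of cured subjects", using Wilson's score method. If that interval "lies entirely above -10% then non-inferiority of the AM schedule is concluded". No stratum or covariate is named.
- **Where species does enter.** Section 8.3.4 uses it as a covariate in the secondary cure-rate model. The Synopsis also attaches a mixed-effects logistic model to the primary hypothesis, but names no species term.
- **PZQ cure rates (1.1.1).** Sh 77.1% (95% CI 68.4-85.1%) and Sm 76.7% (71.9-81.2%). "For mixed Sh/Sm infection, CR was 63.5% (95% CI 48.2-77.0%; 379 participants/6 studies".

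**The concern.** A factor used to stratify the list is normally carried into the primary analysis. If it is left out, the standard error still contains the between-stratum variation that stratification has removed from the estimate, and the interval is wider than it needs to be. Here the whole decision is whether one confidence limit clears -10 points, so any avoidable width costs power.

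The primary population adds a reason. It is per-protocol (8.3.1) and requires attendance at every treatment visit and every four-week assessment. AM children have three courses and PZQ children one, so species balance at randomisation need not survive into the analysed set. A stratified difference corrects for that as far as species is concerned; a crude one cannot.

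The placing of mixed infections is a separate gap. A child with both species must draw an envelope from some stack, and 4.4 gives no rule. The SAP is due only before database lock or any analysis (section 8), whereas strata must be fixed before the first envelope is opened.

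**Working it through.** **1. The plan's own figure.** Section 4.3 sets "at least a 65% cure rate with AM as compared to a 75% cure rate with PZQ", 80% power and 300 per arm. Take a true cure rate of 75% in both arms (equality is not stated), a 10-point margin and one-sided 0.025:

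n = (1.960 + 0.842)^2 x 2 x 0.75 x 0.25 / 0.10^2 = 295 per arm.

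This agrees with 300 to within 3%.

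**2. Variance removed by stratifying.** The mixed share is not given. Assume 40% mixed, 30% Sh only, 30% Sm only, the cited PZQ rates, and the same rates under AM.

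- Overall cure: 0.3 x 0.771 + 0.3 x 0.767 + 0.4 x 0.635 = 0.7154
- Crude variance per child: 0.7154 x 0.2846 = 0.2036
- Within-stratum variance: 0.3 x 0.771 x 0.229 + 0.3 x 0.767 x 0.233 + 0.4 x 0.635 x 0.365 = 0.1993
- Ratio: 0.1993 / 0.2036 = 0.979, a reduction of 2.1%

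With 300 per arm, the half-width 1.96 x sqrt(2 x variance / 300) is 7.22 points crude and 7.14 stratified. Normal-approximation power is 77.5% and 78.3%.

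**3. Simulation.** 100,000 trials per setting, 300 per arm, arms balanced on the three groups, the non-mixed share split equally between Sh and Sm. The crude interval is Newcombe's, built from Wilson limits. The stratified one is a Mantel-Haenszel difference with a normal-theory interval. Distance is the mean from estimate to lower limit, in points. Power is at a true difference of 0.

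| Mixed share (assumed) | Distance, crude / stratified | Power, crude / stratified |
|---|---|---|
| 20% | 6.97 / 6.91 | 80.5% / 80.8% |
| 40% | 7.18 / 7.11 | 78.3% / 78.6% |
| 60% | 7.37 / 7.30 | 76.2% / 76.7% |
| 80% | 7.52 / 7.49 | 74.1% / 74.2% |

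The limit moves by 0.03 to 0.07 point and power by 0.1 to 0.5 point.

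**4. Type I error.** With a true difference of -10 points in every group, one-sided error is 0.0239-0.0253 crude and 0.0244-0.0256 stratified. With no balancing on species at all, the crude error is 0.0250-0.0266. The nominal level is 0.025 and the Monte Carlo standard error is about sqrt(0.025 x 0.975 / 100,000) = 0.0005.

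**5. Larger gaps between groups** (20-60% mixed).

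- Sh 77.1%, Sm 71.9%, mixed 48.2%: stratifying adds 1.5 to 2.4 points of power.
- Sh 85.1%, Sm 81.2%, mixed 48.2% (upper limits for the single species, lower limit for mixed): it adds 2.7 to 4.2 points, and the crude one-sided error falls to 0.018-0.020.

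**The case against.** The strongest reply is that nothing in 8.3.3 is wrong. The crude interval keeps its level, species is examined in the secondary model, and choosing a stratified interval is a matter of efficiency. That stands, and it is why this point is an improvement and not an error. What remains is that the plan stratifies on a factor and then leaves it out of the one interval that decides the trial, although using it needs no new data.

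A reader might infer more in four places, and the protocol does not support it.

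- **That mixed infections have no stratum.** The phrase in 4.4 could mean two crossed yes/no factors, which would give mixed infection its own cell. The text is ambiguous, not shown to be defective.
- **That mixed infections are shown to cure less often.** The gap of about 13 points compares pooled estimates across studies. The intervals overlap, and the mixed one (48.2-77.0%) contains the Sm estimate. The direction is plausible, since cure requires clearing both species, but it is not established.
- **That chance imbalance in mixed infection is an additional harm.** At 40% mixed and without a mixed stratum, the difference in shares has SD sqrt(2 x 0.4 x 0.6 / 300) = 0.04. Times 13.5 points, that shifts the cure difference with SD 0.54 point (95% range about 1.1 points). The crude standard error is 3.68 points, and (0.54 / 3.68)^2 = 2.1%: the same variance component as in step 2, already inside the crude interval.
- **That the gain is larger if AM works differently by species.** AM cure of 80/50/35% (Sh/Sm/mixed, assumed) would give an 8.7% variance reduction. But AM then averages 0.3 x 80 + 0.3 x 50 + 0.4 x 35 = 53.0% against 71.5%, a true difference of -18.5 points, where non-inferiority fails with either interval.

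**Conclusion.** The point holds as a free improvement with a small gain. The primary interval ignores the randomisation factor, remains valid, and is slightly conservative when arms are balanced on species. With the cited point estimates, 300 per arm, no true difference and an assumed 20-80% mixed share, stratifying brings the lower limit in by under 0.1 point and adds at most about 0.5 point of power in simulation (0.8 on the normal approximation at 40% mixed). A gain of 2.7-4.2 points needs cure rates at opposite ends of the cited intervals. Type I error is not inflated.

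The fall in power down the table, from about 80% to 74%, should not be read as the cost of omitting strata. It comes from the lower overall cure rate as the mixed share rises, and stratifying does not recover it.

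The rule for placing mixed infections is an ambiguity to settle before randomisation starts.

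**What to change.** - **4.4.** State the strata as Sh only, Sm only and mixed. Say which microscopy result assigns a child. Section 5.1 takes a first sample at screening and repeats sampling and microscopy at recruitment, where randomisation takes place, so a child could be single-species on one and mixed on the other.
- **8.3.3.** Base the non-inferiority decision on a risk difference stratified over those three groups, with Mantel-Haenszel weights and a stratified Newcombe or Miettinen-Nurminen 95% CI against the same -10-point margin. Keep the crude Wilson-score interval as a sensitivity analysis.

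The cost is a sentence or two in each section. The microscopy is already scheduled before treatment, so no extra data or participants are needed. If randomisation has already begun, the list cannot be changed, but the rule actually used should be documented and the analysis strata defined from pre-randomisation microscopy before any outcome is analysed.

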4.5. Withdrawal and termination of the study

Reasons for withdrawal

Participants may be withdrawn from the study if:

- The parents/guardians of the participant withdraw the consent
- The participant develops epilepsy, psychiatric illness or severe gastric intolerance, or any other illness that could have a negative effect on the participant's health before the last dose of study medication
- The participant has vomited the initial and repeated dose of study medication
- The participant needs to get started on chronic medication for any reason before the last dose of study medication

Participants will only be considered lost-to-follow up after the week 48 follow-up visit window has passed. Participants who miss one or more study visits will remain in the study. The missed visits will be skipped, and the participant will continue with the original visit schedule (see chapter 5). Participants will be actively followed-up to attend all study visits.

Handling of Withdrawals

Participants withdrawing for medical reasons will be referred to adequate health facilities for further care if necessary.

Unless consent is withdrawn, efforts will be made to schedule, for these participants, at least the week 24 and week 48 follow-up visits. Collection and follow-up of adverse events and serious adverse events is further described in chapter 7.

Participants who have been withdrawn from the study will be offered a standard dose of PZQ.

Data collected up to the time of withdrawal will remain in the study data base and be used for analysis whether or not the participant continues with the follow-up visits.

Termination of study

In case the members of the DSMB (see chapter 7.2), based on preliminary data presented to them, show concern about the continuation of the trial (for safety or any other reason) they may collectively advice the Sponsor to prematurely terminate the study. Following ethical shortcomings in the conduct of the project, the ethics committees in Senegal or Belgium could also decide to stop the study.

If the study is prematurely terminated or suspended, the Sponsor will promptly inform the investigators/institutions, and the regulatory authority(ies) of the termination or suspension and the reason(s) for the termination or suspension. The ECs will also be informed promptly and provided the reason(s) for the termination or suspension by the Sponsor or by the investigator/institution, as specified by the applicable regulatory requirement(s).

5. STUDY PROCEDURES

5.1. Study/visit schedule

Screening

- Informed consent procedure and signing the ICF by parents/guardians
- First urine and stool sampling for investigation of schistosomiasis
- Eligibility screening (inclusion/exclusion criteria):
 - Collection of demographics and medical history data

Recruitment

- Medical evaluation, with special emphasis on exclusion criteria
- Ultrasound examination (by a radiologist experienced in *Schistosomiasis* assessment)
- Blood (finger prick)*, urine and stool sampling**
- Hemoglobin measurement
- Parasitological assessment by microscopy and POC-CCA
- Urine reagent strip testing
- Point-of-care fecal occult blood
- Randomization in the AM or PZQ arm

First administration of IMP (Day 0)

- Systematic questionnaire on concomitant medication and symptoms
- Administration of study medication, under directly observed therapy:
 - AM arm: first dose of A at 4 mg/kg and M at 8 mg/kg
 - PZQ arm: single dose of PZQ (40 mg/kg)

First administration of the IMP (Day 1 & 2) (AM arm only)

- Administration of study medication in AM arm: second and third doses of A at 4 mg/kg and M at 8 mg/kg
 - Follow-up for AE and SAEs***

Follow-up for AE and SAE (Day 7)

- Systematic questionnaire on concomitant medication, symptoms and malaria diagnosis

Evaluation of parasitological efficacy after initial treatment (week 4)

- Urine and stool sampling**
- Parasitological assessment by microscopy and POC-CCA
- Systematic questionnaire on concomitant medication, symptoms and malaria diagnosis
- Follow-up for AEs and SAEs*** (retrospective assessment)

Second administration of the IMP, day 0 (AM arm only) (week 6)

- Systematic questionnaire on concomitant medication, symptoms and malaria diagnosis
- Administration of study medication in AM arm: first dose of A at 4 mg/kg and M at 8 mg/kg

Second administration of the IMP, day 1 & 2 (AM arm only) (week 6)

- Systematic questionnaire on concomitant medication and symptoms
- Administration of study medication in AM arm: second and third doses of A at 4 mg/kg and M at 8 mg/kg
- Follow-up for AE and SAEs***

Follow-up for AE and SAE (Day 7)

- Systematic questionnaire on concomitant medication, symptoms and malaria diagnosis *Evaluation of parasitological efficacy after second round of AM (week 10)*

- Urine and stool sampling**
- Parasitological assessment by microscopy and POC-CCA
- Systematic questionnaire on concomitant medication, symptoms and malaria diagnosis
- Follow-up for AEs and SAEs***

Third administration of the IMP, day 0 (AM arm only) (week 12)

- Systematic questionnaire on concomitant medication, symptoms and malaria diagnosis

- Administration of study medication in AM arm: first dose of A at 4 mg/kg and M at 8 mg/kg *Third administration of the IMP, day 1 & 2 (AM arm only) (week 12)*
 - Systematic questionnaire on concomitant medication and symptoms
 - Administration of study medication in AM arm: second and third dose of A at 4 mg/kg and M at 8 mg/kg
 - Follow-up for AE and SAEs***

Follow-up for AE and SAE (Day 7)

- Systematic questionnaire on concomitant medication, symptoms and malaria diagnosis *Evaluation of parasitological efficacy after third round of AM (week 16)*
 - Systematic questionnaire on concomitant medication, symptoms and malaria diagnosis
 - Urine and stool sampling**
 - Parasitological assessment by microscopy and POC-CCA
 - Follow-up for AEs and SAEs***

Intermediate evaluation of clinical efficacy (week 24)

- Systematic questionnaire on concomitant medication, symptoms and malaria diagnosis
- Medical evaluation
- Ultrasound examination
- Blood (finger prick)*, urine and stool sampling**
- Hemoglobin measurement
- Parasitological assessment by microscopy and POC-CCA
- Urine reagent strip testing
- Point-of-care fecal occult blood

Final evaluation of clinical efficacy (week 48)

- Systematic questionnaire on concomitant medication, symptoms and malaria diagnosis
- Medical evaluation
- Ultrasound examination
- Blood (finger prick)*, urine and stool sampling**
- Hemoglobin measurement
- Parasitological assessment by microscopy and POC-CCA
- Urine reagent strip testing
- Point-of-care fecal occult blood
- PZQ for all the children enrolled in the study and MDA to the rest of the community under the coordination of the national control program, according to WHO guidelines^{74,75}

A schematic overview of the visit schedule and related procedures can be found in the 'Table 1: Schedule of assessments' below.

* Dried blood spot (DBS) will also be collected on filter papers and will be shipped to ITM for further molecular analysis (malaria diagnosis and presence of mefloquine resistance markers / markers of susceptibility to artemisinin)

** Urine and stool samples will be aliquoted, preserved and shipped to ITM for further schistosomiasis diagnostic assays (eg. urine CAA lateral-flow assay – UCP-LF CAA – and a real-time stool and urine PCR) *** Throughout the trial, (S)AEs up until 4 weeks after the last administration of study medication (PZQ and AM arm) will be taken into account. In the AM arm, on the second and third administration day, this will be actively monitored. Plus, for both arms, efforts will be made to proactively monitor the adverse events within one week after PZQ and first AM administration, by an additional visit at day 7. If no contact is possible, (S)AEs will be gathered at the next scheduled study visit. More details on safety collection and reporting are described in chapter 7. A study specific SOP will be created to elaborate on the detection, the handling, and the reporting of AEs and SAEs.

Table 1: Schedule of assessments

		Screening	Recruitment	1 st admin IMP (Day 0)	1st admin IMP (Day 1 & 2³)	Follow-up AE & SAE Day 7	Parasitologic al evaluation 1	2 nd admin IMP, day 0 ³	2 nd admin IMP day 1 & 2 ³	Follow-up AE & SAE Day 7	Parasitologic al evaluation 2	3 rd admin IMP, day 0 ³	3 rd admin IMP day 1 & 2 ³	Follow-up AE & SAE Day 7	Parasitologic al evaluation 3	Intermediar efficacy evaluation	Final efficacy evaluation
Informed consent		Х															
Eligibility		Х	Х														
Demographics		Х															
Medical history			Х														
Medical evaluatio	n		Х													Х	х
Hemoglobin meas	urement		Х													Х	х
Microscopy (urine	and stool)	Х	Х				Х				х				х	Х	х
POC-CCA			Х				Х				х				х	Х	х
Urine reagent stri	o test		Х													Х	х
Fecal occult blood			х													Х	х
Ultrasound			Х													Х	х
Randomization			Х														
Concomitant med	ication check			Х	Х	Х	х	Х	х	Х	х	Х	х	Х	х	Х	х
Symptom check				Х	Х	Х	х	Х	х	Х	х	Х	х	Х	х	Х	х
Malaria diagnosis	check					Х	Х	Х		Х	х	Х		Х	Х	Х	Х
Study drug administration	AM arm			AM	AM			AM	AM			AM	AM				PZQ
	PZQ arm			PZQ													PZQ
(S)AE follo	w-up				X1	Х	Х		X1	Х	Х		X1	Х	Х		

 1 (S)AE follow-up done before second and third study drug administration.

² (S)AE follow-up done up to 4 weeks after the last study drug administration. However, efforts will be made to proactively monitor the adverse events within a week after PZQ and each AM administration, by an additional visit at day 7. If participants could not be reached, (S)AEs will be collected during the study visit. ³ Only applicable for AM arm

